4.2 EXCLUSION CRITERIA

- 1. No prior irinotecan or carfilzomib
- 2. Must not have evidence of leptomeningeal metastases.
- 3. Must be no anticipated need for concurrent radiation therapy during protocol treatment.
- 4. Subjects that progressed during or within one month of completion of first-line platinumbased chemotherapy will be excluded.
- 5. Subjects must not be pregnant or lactating females.
- 6. Must have had no major surgery within 28 days prior to enrollment to treatment.
- 7. Must not have acute active infection requiring treatment (systemic antibiotics, antivirals, or antifungals) within 14 days prior to enrollment to treatment.
- 8. Must not have known human immunodeficiency virus infection.
- 9. Must not have known active or clinically significant hepatitis A, B or C infection.
- 10. Must not have had any unstable angina or myocardial infarction within 4 months prior to enrollment to treatment, NYHA Class III or IV heart failure, uncontrolled angina, history of severe coronary artery disease, severe uncontrolled ventricular arrhythmias, sick sinus syndrome, or electrocardiographic evidence of acute ischemia or Grade 3 conduction system abnormalities unless subject has a pacemaker.
- Must not have any uncontrolled hypertension or uncontrolled diabetes within 14 days prior to enrollment to treatment.
- 12. Must not have any evidence of moderate or severe pulmonary hypertension.
- 13. Must not have any evidence of other clinically active cancer and have no history of prior malignancy within the past 3 years with the exception of a) adequately treated basal cell carcinoma, squamous cell skin cancer, or thyroid cancer; b) carcinoma in situ of the cervix or breast; c) prostate cancer of Gleason Grade 6 or less with stable prostate-specific antigen levels; or d) cancer considered cured by surgical resection or unlikely to impact survival

during the duration of the study, such as localized transitional cell carcinoma of the bladder or benign tumors of the adrenal glands or pancreas.

- 14. Must not have any significant neuropathy (Grades 3–4, or Grade 2 with pain) within 14 days prior to enrollment to treatment.
- 15. Must not have any known history of allergy to Captisol[®] (a cyclodextrin derivative used to solubilize carfilzomib).
- 16. Must have no contraindication to any of the required concomitant drugs or supportive treatments, including hypersensitivity to all anticoagulation and antiplatelet options, antiviral drugs, or intolerance to hydration due to preexisting pulmonary or cardiac impairment.
- 17. Must not have any other clinically significant medical disease or condition that, in the Investigator's opinion, may interfere with protocol adherence or a subject's ability to give informed consent.

4.3 STRATIFICATION FACTORS FOR PHASE II COMPONENT:

In the phase II component of the study, subjects will be stratified according to the following: **Platinum sensitive disease**: an initial response to platinum-based chemotherapy with subsequent progression observed greater than 90 days after last platinum treatment OR

Platinum refractory disease: No response to platinum-based chemotherapy or progression within 90 days of completing platinum-based therapy. Subjects that progressed during or within one month of completion of platinum-based chemotherapy will be excluded.

5 SUBJECT REGISTRATION/ENROLLMENT

Eligible subjects must be registered within 3 working days prior to initiation of protocol chemotherapy.

This study uses a web based subject registration/enrollment system for data submission, through the data management services of Cancer Research And Biostatistics (CRAB). The subject registration ("registration") form is accessed online through the study website https://ctc-11-001.crab.org/Login.aspx. Access is protected and available to authorized users only. For questions or assistance using this site, please contact: [contact].

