- Grade 3 nausea, vomiting or diarrhea (unless persisting > 3 days with adequate treatment of antiemetics or anti-diarrheals)
- Grade 3 fatigue (unless persisting for >14 days)

Neither Carfilzomib nor Irinotecan need to be held in the following cases:

- Alopecia
- \geq Grade 3 hyperglycemia attributed to dexamethasone

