6.5.3 EXCLUDED CONCOMITANT MEDICATIONS

Concurrent therapy with other investigative anticancer therapies or other investigational agents is not allowed.

7 STUDY TESTS AND OBSERVATIONS:

Phase Ib Study Calendar:

Required Studies		Cycle 1			Cycle 2,4,6					Cycle 3, 5												
-		Day			Day																	
	Screen within 2weeks unless specified	1	2	8	9	15	16	1	2	8	9	15	16	22	1	2	8	9	15	16	Off study	Follow-up [@]
PHYSICAL																						
Informed Consent	X																					
Medical History	X																					
Physical Examination	X							X							X						X	X
Performance Status and Weight	X							X							X						X	X
Toxicity Assessment								X							X						X	X
Disease Assessment	X							X							X							
RADIOLOGY																						
CT/MRI scan ¶	X													X							X	X
Brain CT/MRI #	Х																					
ECG#	Х																					
LABORATORY																						
CBC w/differential	X*	X		X		Х		X		X		X			X		X		X		X	X
Serum chemistries §	X*	X		X		X		X		X		X			X		X		X		X	X
Serum Magnesium	X*	X						X							X						X	X
Serum or urine Pregnancy Test	X*																					
TREATMENT																						
Irinotecan √		X		X		X		X		X		X			X		X		X			
Carfilzomib $$ (study provided)		X	X	X	X	Х	X	X	X	X	X	X	X		X	X	X	X	X	X		
Dexamethasone 8 mg ⁺		X	X	X	X	X	X															
PD/Correlative																						
Pharmcodynamic blood tests £		X	X																			
Tissue Submission &	X			1														1				

¶ CT or MRI (the same method used at prestudy to meet the eligibility criteria in Section 5.3) must be repeated every8 weeks until disease progression. Once off study, the frequency of this scan may be reduced to every 3 months until disease progression.

#Prestudy, and then as clinically indicated

* This test is required prestudy within 2 weeks of starting study medication.

§ Sodium, potassium, calcium, chloride, creatinine, magnesium, SGOT, SGPT, alkaline phosphatase, total bilirubin prior to treatment on Day 1 of each cycle (at most 2 days prior to Day 1 of the next cycle); Sodium, potassium, chloride, creatinine, prior to treatment on Day 8 & 15

√ After completion of Cycle 6 and if the subject has not met criteria for disease progression, carfilzomib and irinotecan may be continued at the discretion of the sponsor and treating physician.

+ Dexamethasone 8 mg prior to all carfilzomib doses during the first cycle and after that as per section 6.5.1.

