£ PD: Carfilzomib proteasome chymotrypsin-like activity in PBMC (LMP7 and b5 activity) and gamma-H2AX and Topoisomerase-I expression Day 1: The sampling times relative to the start of irinotecan infusion: Pre-irinotecan, 90 min, 2 hours, 5.5 hours; Day 2: pre-carfilzomib infusion

& Submit tumor block or 10 unstained slides of pre-existing tumor

@ Follow-up will be for 30 days after last treatment or until all drug-associated (possible, probably or definite) toxicities have resolved to Grade 1 or less

Phase II Study Calendar:

Required Studies		Cycle 1				Cycle 2,4,6					Cycle 3, 5											
-			Day Day																			
	Screen within 2 weeks unless specified	1	2	8	9	15	16	1	2	8	9	15	16	22	1	2	8	9	15	16	Off study	$Follow-up^{@}$
PHYSICAL																						
Informed Consent	X																					
Medical History	Х																					
Physical Examination	X							Х							Х						Х	Х
Performance Status and Weight	Х							Х							Х						Х	Х
Toxicity Assessment								Х							Х						Х	Х
Disease Assessment	X							Х							Х							
RADIOLOGY																						
CT/MRI scan ¶	Х													Х							Х	Х
Brain CT/MRI #	Х																					
ECG#	X																					
LABORATORY																						
CBC w/differential	X*	Х		Х		х		Х		Х		Х			Х		Х		Х		Х	Х
Serum chemistries §	X*	Х		Х		Х		Х		Х		Х			Х		Х		Х		Х	Х
Serum Magnesium	X*	Х						Х							Х						Х	Х
Serum or urine Pregnancy Test	X*																					
TREATMENT																						
Irinotecan √		Х		Х		Х		Х		Х		Х			Х		Х		Х			
Carfilzomib $$ (study provided)		Х	Х	Х	Х	х	Х	Х	Х	Х	х	Х	Х		Х	Х	Х	Х	Х	Х		
Dexamethasone 8 mg		Х	Х	Х	Х	Х	Х															
PK/PD/Correlative																						
Pharmcodynamic blood tests £		X	Х																			
Tissue Submission &	X			1				1		1					1			1				ĺ

¶ CT or MRI (the same method used at prestudy to meet the eligibility criteria in Section 5.3) must be repeated after ever two cycles of treatment until disease progression. Once off study, the frequency of this scan may be reduced to every 3 months until disease progression.

#Prestudy, and then as clinically indicated

* This test is required prestudy within 2 weeks of starting study medication.

§ Sodium, potassium, calcium, chloride, , creatinine, magnesium, SGOT, , alkaline phosphatase, total bilirubin prior to treatment on Day 1 of each cycle (at most 2 days prior to Day 1 of the next cycle); Sodium, potassium, chloride, creatinine, prior to treatment on Day 8 & 15

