		the blood	pale stools which	
			may be caused by a blockage in the	
			flow of bile from	
			the liver (cholestasis)	
Infections	Respiratory tract	Sore throat;		
	infection;	Bronchitis;		
	Pneumonia	Runny nose or nasal congestion;		
		Urinary tract infection;		
		Inflammation of		
		the nose and throat;		

System	(may affect more than 1 in 10 people)	(may affect up to 1 in 10 people) Flu-like symptoms (influenza); Serious infection in the blood (sepsis); Viral infection; Infection and/or irritation of your stomach and bowels;	(may affect up to 1 in 100 people)	(may affect up to 1 in 1000 people)
		Lung infection		
Metabolism	Decreased appetite	Dehydration	Tumor lysis syndrome (TLS) (see "Conditions you need to look out for')	
Bone and Muscle	Back pain; Joint pain; Pain in limbs, hands or feet; Muscle spasms	Bone and muscle pain; Chest pain; Muscle weakness; Aching muscles		
Nervous System	Headache; Dizziness; Numbness	Abnormal sensation such as tingling or decreased sensation in arms and/or legs	Bleeding in the brain	Posterior reversible encephalopathy syndrome (PRES) (see 'Conditions you need to look out for')
Psychiatric	Insomnia (difficulty sleeping)	Anxiety		
Kidney Skin		Kidney problems, including decreased ability to make urine, increased creatinine in the blood, and kidney failure needing dialysis		

Body System	Very Common (may affect more than 1 in 10 people)	Common (may affect up to 1 in 10 people)	Uncommon (may affect up to 1 in 100 people)	Rare (may affect up to 1 in 1000 people)
		ltchy skin; Redness of the skin; Increased sweating		
Tests	Changes to blood tests (decreased blood levels of potassium, increased blood levels of sugar and/or creatinine)	Changes to blood tests (decreased blood levels of sodium, magnesium, protein, calcium or phosphate, increased blood levels of calcium, uric acid, potassium, bilirubin, or c- reactive protein)		
Immune System			Allergy to carfilzomib	
Blood Vessels	High blood pressure (hypertension)	Low blood pressure (hypotension); Blood clots in the veins; Flushing	Stroke; Bleeding; Extremely high blood pressure (see 'Conditions you need to look out for')	
Ear and labyrinth		Ringing in the ears		

*The risk of developing heart failure when receiving carfilzomib is higher if you are 75 years of age or older. This risk is also higher if you are Asian.

Subjects will be advised to inform the study staff if they develop any of the following:

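### No legible scheduled chemistry list names glucose, so the diabetes exclusion, the hyperglycemia exception and the Grade 3–4 laboratory recording rule cannot be applied from scheduled laboratory data

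*Combined protocol and SAP*

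**What the plan says.** Four provisions depend on knowing a subject's glycemic state.

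- **Section 4.2, exclusion 11:** "Must not have any uncontrolled hypertension or uncontrolled diabetes within 14 days prior to enrollment to treatment". No glucose or HbA1c threshold is given.
- **Section 6.3.5.8:** under the lead-in "Neither Carfilzomib nor Irinotecan need to be held in the following cases", the list includes, for that grade and above, "Grade 3 hyperglycemia attributed to dexamethasone".
- **Section 9.3.1, Tests row:** the column for effects seen in more than 1 in 10 people includes "increased blood levels of sugar and/or creatinine", alongside low potassium.
- **Section 9.3:** every Grade 3 or 4 laboratory abnormality goes on the CRF as an adverse event. Lower grades are entered only when treated or judged clinically important.

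Section 7 sets out what is measured. The serum chemistry row of both calendars is marked at screening, on Days 1, 8 and 15 of each cycle, at off-study and at follow-up. A footnote names the analytes:

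- **Phase Ib, Day 1:** "Sodium, potassium, calcium, chloride, creatinine, magnesium, SGOT, SGPT, alkaline phosphatase, total bilirubin prior to treatment on Day 1 of each cycle"
- **Phase II, Day 1:** "Sodium, potassium, calcium, chloride, , creatinine, magnesium, SGOT, , alkaline phosphatase, total bilirubin prior to treatment on Day 1 of each cycle"
- **Days 8 and 15, same wording in both phases:** "Sodium, potassium, chloride, creatinine, prior to treatment on Day 8 & 15"

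Sections 6.1 and 6.5.1 give dexamethasone 8 mg before each carfilzomib dose in Cycle 1. Section 6.5.1 permits a higher dose under institutional practice, and re-institution later if infusion-type symptoms occur.

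**The concern.** The protocol expects hyperglycemia. It gives a steroid repeatedly in Cycle 1, lists raised blood sugar as a frequent laboratory change with the study drug, and writes a specific exception for it. It does not schedule the measurement that would show whether hyperglycemia has occurred.

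Safety and tolerability, including rates of specific adverse events, are Phase II secondary endpoints (Section 11). If an event without symptoms is found only when a site happens to measure glucose, the reported rate reflects local testing habits as well as the drugs. With at least 8 sites planned (Section 3.2), those habits need not be uniform. At entry, diabetes control has no required objective measure, whereas renal, hepatic and hematologic function have explicit laboratory thresholds in Section 4.1.

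**Working it through.** No design figure for hyperglycemia exists to reproduce, so the check is mainly a comparison of passages.

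**1. Is glucose on any scheduled list?**

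- Phase Ib, Day 1 of each cycle: 10 analytes, list intact, no glucose.
- Phase II, Day 1 of each cycle: 9 legible analytes, no glucose. There are two empty positions. The one after SGOT matches SGPT in the Phase Ib list. The one after chloride has no counterpart there and cannot be identified.
- Days 8 and 15, both phases: 4 analytes, list intact, no glucose.
- Screening, off-study and follow-up: the chemistry row is marked, but no separate panel is itemised.

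The other laboratory rows are blood count, magnesium and a pregnancy test. No other section schedules glucose or HbA1c.

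**2. Which provisions need a glucose value?** Besides the four already listed, Section 6.3.3 (other drug-related toxicity of Grade 3 or higher) and the laboratory note in the Section 6.2.2 definition of dose-limiting toxicity would cover hyperglycemia not attributed to dexamethasone. Section 1.5 reports that Phase Ib enrollment is complete, so the part that can still be changed is Phase II.

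**3. What would the existing draws show?** Protocol dexamethasone in Cycle 1 falls on Days 1, 2, 8, 9, 15 and 16, and chemistry is drawn before treatment.

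- Cycle 1 Day 1: before any protocol dexamethasone.
- Day 8: 8 − 2 = 6 days after the last dose.
- Day 15: 15 − 9 = 6 days after the last dose.
- Cycle 2 Day 1, on the 28-day schedule: 29 − 16 = 13 days after the last Cycle 1 dose, or 11 if drawn the permitted 2 days early.

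These draws can show baseline and persistent hyperglycemia. They are poorly placed for a short rise after a steroid dose.

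**4. Can the shortfall be sized?** Section 11 says adverse event rates can be estimated to within at most ±16% per stratum. That reproduces: 1.96 × √(0.5 × 0.5 / 40) = 0.155. It covers sampling error only and assumes every event is found. If a proportion p of n subjects have a recordable event and a proportion s of these are found without scheduled testing, the expected number missed is n × p × (1 − s). The documents give neither p nor s. Purely to show the dependence, with n = 40 and assumed values:

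- p = 5%: 1.5 missed at s = 25%, 0.5 at s = 75%
- p = 10%: 3.0 and 1.0
- p = 20%: 6.0 and 2.0

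At s = 100% nothing is missed. The assumptions determine the answer, so no estimate is offered.

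**The case against.** The best case on the other side is that the calendar sets a minimum. It does not bar a local metabolic panel or a test on clinical grounds, and Section 9.1 treats any unfavorable laboratory finding as an adverse event. Diabetes control can be judged from the medical history and physical examination required at screening, and from concomitant medications recorded from 14 days before Day 1. HIV, hepatitis and pulmonary hypertension are also excluded without a specific scheduled test. Recording Grade 3 and 4 abnormalities does not oblige a protocol to schedule every analyte. All of this stands, and it limits the point to the completeness and uniformity of ascertainment.

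It also rules out several stronger readings that a reader might infer:

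- **That the hyperglycemia rule cannot fire.** Section 6.3.5.8 is an exemption from holding. An unmeasured dexamethasone-related value leads to the same action as a measured one: neither drug need be held.
- **That more than 4 of 40 subjects per stratum, or 8 of 80, would go undetected.** This takes 10% as a floor for raised glucose. The Section 9.3.1 cell pools potassium, sugar and creatinine and gives no grade, while Section 9.3 limits recording of Grade 1 and 2 values. (Section 9.1 asks for all grade changes, laboratory values included, which fits awkwardly with that limit.) No Grade 3–4 rate is given.
- **That the trial never measures glucose, or that exclusion 11 cannot be applied.** Unscheduled testing is open to sites, and the exclusion can be applied on clinical judgement.
- **That every list, screening included, omits glucose.** No screening list exists, and one slot in the Phase II Day 1 list is unreadable.

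**Conclusion.** The point holds as a gap in safety ascertainment. The provisions that turn on glycemia cannot be applied from scheduled laboratory data, because no legible scheduled list contains glucose. The Phase Ib Day 1 list and the Day 8 and 15 lists are intact, so the finding does not rest on lost text alone; only the Phase II Day 1 entry carries doubt.

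The direction is clear. Missing measurement can lower the count of asymptomatic events but cannot raise it. Under-ascertainment that varies by site is therefore likely, on the assumption that sites differ in unscheduled glucose testing. Its size cannot be calculated from the documents.

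A reader might also infer a threat to the maximum tolerated dose or to the efficacy decision. The documents do not support that. A laboratory value counted as dose-limiting only if clinically significant and related, and nothing indicates that such an event was missed. The primary endpoint is being alive at six months, which does not depend on glucose.

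**What to change.** For Phase II:

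- Add glucose to the serum chemistry footnote in Section 7 at the existing Day 1, Day 8 and Day 15 draws.
- Add it at screening, and state which analytes make up the screening panel.
- Fill or remove the two empty positions in the Phase II Day 1 list. If the unidentified one was glucose, that part is already met and only the other time points need the change.
- Add an eCRF field for the result.
- Reconcile the footnote with exclusion 11, Section 6.3.5.8 and the Section 9.3 recording rule. Leave all dose, hold and steroid rules as they are.

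If the sponsor prefers not to add the analyte, the protocol should say how glycemia is assessed, and the report should state that hyperglycemia was not systematically measured.

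The cost is one assay and one data field per draw, on blood already taken, with no extra visit or procedure. The limitation is timing: pre-dose draws will mainly detect baseline and persistent hyperglycemia, so short peaks after dexamethasone will still largely go unseen.

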6 TREATMENT PROCEDURES

6.1 DRUG PREPARATION AND ADMINISTRATION.

- **Carfilzomib** for Injection is supplied as a lyophilized parenteral product in single-use vials. The lyophilized product is reconstituted with Sterile Water for Injection to a final carfilzomib concentration of 2.0 mg/mL prior to administration. Refer to Study Manual for full instructions. The dose will be calculated using the subject's actual BSA at baseline, or Day 1. Subjects with a BSA > 2.2 m² will receive a dose of carfilzomib based upon a 2.2 m² BSA.
- For subjects considered at risk for TLS, oral hydration may be given as follows:
 30 mL/kg/day (approximately 6 to 8 cups of liquid per day) continuing up to the time of treatment.
- IV hydration will be given prior to carfilzomib during Cycle 1. This will consist of 250 to 500 mL normal saline or other appropriate IV fluid given over 30 to 60 minutes. If lactate dehydrogenase (LDH) or uric acid is elevated > 1.5 times IULN (and/or in subjects considered still at risk for TLS) at Cycle 2 Day 1, then the recommended IV hydration should be given additionally before each dose in Cycle 2. The goal of the hydration program is to maintain robust urine output (e.g., ≥ 2 L/day). Subjects should be monitored periodically during this period for evidence of fluid overload. Note: On Days 1, 8 and 15 of cycle 1, irinotecan is given prior to carfilzomib and this satisfies the prehydration requirement, provided the irinotecan is mixed in at least 250 mL of fluid.
- If the subject has a dedicated line for carfilzomib administration, the line must be flushed with a minimum of 20 mL of normal saline prior to and after drug administration.
- Dexamethasone 8 mg PO/IV will be administered prior to all carfilzomib doses during Cycle 1 and after that as described in section 6.5.1.
- Carfilzomib will be given as an IV infusion over approximately 30 minutes. The dose will be administered at a facility capable of managing hypersensitivity reactions. Subjects will remain at the clinic under observation for at least 1 hour following each dose of carfilzomib in Cycle 1 and following the dose on Cycle 2 Day 1. During these observation times, **post dose IV** hydration (between 250 mL and 500 mL normal saline or other appropriate IV fluid formulation) may be given over 30 to 60 minutes. Subjects should be monitored periodically during this period for evidence of fluid overload.

- Irinotecan is commercially available and supplied in amber vials and appears as a pale yellow ٠ transparent solution. Two vial sizes are available: 2 ml vials containing 40 mg of drug and 5 ml vials containing 100 mg of drug. Prior to administration, irinotecan will be diluted with 5% dextrose in water (preferred diluent) or 0.9% sodium chloride solution to a total volume of 250-500 ml (final concentration of 0.12 to 2.8 mg/ml). Irinotecan will be administered intravenously over 90 minutes prior to Carfilzomib infusion.
- Dose adjustments for Carfilzomib or Irinotecan do not need to be made for weight gain/loss of < 10%

6.2 TREATMENT PLAN

6.2.1	PHASE I POR	FION OF THE STUDY	
ACENT	DOSE	DOUTE	D

AGENT	DOSE	ROUTE	DAYS	INTERVAL
Irinotecan	125 mg/m ²	IV infusion (over 90 min)	1, 8, 15	q 28 days
Carfilzomib	$20/*mg/m^2$	IV infusion (over 30 min)	1, 2, 8, 9 15 and 16	q 28 days

* Cycle 1 Day 1 & Day 2 doses are 20 mg/m2. All subsequent days as specified, i.e. 20/27 mg/m2 means Cycle 1 Day 1 & Day 2 doses are 20 mg/m2 and all other days are 27mg/m2.

Dosage schedule, phase 1b:

	Doses		
3+3 design	Carfilzomib*	Irinotecan	
Cohort -2	20 mg/m^2	75 mg/m^2	
Cohort -1	20 mg/m^2	100 mg/m^2	
Cohort 1	$20/27 \text{ mg/m}^2$	125 mg/m^2	
Cohort 2	20/36 mg/m ²	125 mg/m^2	
Cohort 3	$20/45 \text{ mg/m}^2$	125 mg/m ²	
Cohort 4	20/56 mg/m ²	125 mg/m^2	
Cohort 5	20/70 mg/m ²	125 mg/m^2	
* Cycle 1 Day 1 & Day 2 doses are 20 mg/m2. All subsequent days as specified,			

other days are 27mg/m2.

Additional cycles of therapy may be administered provided the subject meets all of the following at the beginning of each cycle prior to treatment on Day 1 (at most 2 days prior to Day 1 of the next cycle):

- ANC $\ge 1,500/\mu L$. •
- Platelet count $\geq 100,000/\mu$ L.

- All other Grade 2, 3 or 4 non-hematological toxicities have resolved as required in section 6.3.3.
- Serum creatinine ≤ 1.5 x IULN OR measured or calculated creatinine clearance ≥ 60 mL/min using the Cockcroft-Gault.

